The Restorative Activities Scale will be used to assess the frequency of engaging in restorative activities. Restorative activities refer to activities that rejuvenate or restore individuals to some equilibrium such as value hobby, physical exercise, or sleep. Restorative activities have been linked to both improved mental and physical health outcomes.

Coping Flexibility

The **Frankfort Monitoring Blunting Scale** (FMBS) ¹²⁸ is designed to assess rigid vs. adaptive coping styles. Rigid coping refers to either Monitoring or Blunting in situations implying threat and thereby disregarding situational control contingencies. Adaptive coping pertains to the employment of Monitoring strategies in controllable situations and Blunting strategies in uncontrollable situations. The FMBS is composed of four uncontrollable and threatening vignettes (waiting for surgery, threat ¹²⁹ of being laid off work, turbulent flight, being stuck in an elevator) and four controllable and stressful vignettes (important job interview, icy road conditions, losing one's way in New York City, applying for a mortgage). Controllability is defined as the possibility to change the outcome of a situation through active intervention. Each FMBS situation is followed by eight behavioral choices. Of these, four items pertain to a Monitoring (information seeking) and four to a Blunting (reinterpretation of and distraction from the threatening aspects of a situation) style of coping with aversive events. Participants are instructed to respond to each item on a four-point rating scale (1 = complete disagreement, 4 = complete agreement). Individuals are classified as rigid "monitors" (high monitoring scores in controllable and uncontrollable situations) or "blunters" (high blunting scores in controllable and uncontrollable situations) or "adaptive copers" (high monitoring scores in controllable situations and high blunting scores in uncontrollable situations) or "unspecified types" on the basis of their scores. Unspecified types refer to participants who are neither monitors nor blunters nor adaptive copers.

Concomitant Medications

The names and dosing regimens of all medications and significant non-drug therapies (e.g. physical therapy, dietary supplements, OTC agents) administered after the patient begins treatment will be recorded (week 1, 3, 5, 7, 8, 10) and at each follow-up assessment period on the Concomitant Medications Log.

Follow-up Assessments

The IBSOS is designed to assess both the immediate and long-term follow-up benefits of CBT for IBS, as well as its clinical course. To achieve these objectives, it is essential that each participant be examined regularly at follow-up visits until the study is terminated. Follow-up assessments are scheduled two weeks after treatment ends and every three months thereafter (three, six, nine, and 12 months).

Study Visit Windows

Follow-up assessments will be conducted in person, at appointments scheduled by the PC specifically for this purpose. Scheduling should occur by telephone when possible; participants who do not have telephones will be contacted by mail and asked to make arrangements for an appointment. Participants may also make appointments in person. A minimum of three contact attempts should be made and documented before a patient is considered unreachable. If a patient cannot be contacted, inform the SI after two attempts have been made, and before ruling a patient unreachable. Every conceivable effort must be made before a participant is deemed unreachable. Participants who are lost to follow-up during the active treatment phase, however, are allowed and should be encouraged to participate in regularly scheduled follow-up assessments. *All participants, regardless of whether or not they completed therapy, should be contacted for all follow-up assessments and compensated for their time.*

We ask that every effort be made to adhere to the specific time windows when performing the follow-up assessments. If this is not possible, the window can be extended for purposes of recording the visit. However, **extensions should be** *regarded as the exception and not the rule.*

- Two-week post-treatment Post-treatment assessment should occur two weeks following the end of active therapy. However, it is permitted for post-treatment follow-up visits to occur within the two weeks preceding or following the scheduled appointment (i.e. weeks 10-14).
- Interim assessment Participants will describe their daily bowel habits using the Bristol Stool form and rate the intensity of pain, bloating, and urgency (11-point VAS) at the end of each day through the 10-week acute treatment phase. At the end of each week of the acute treatment phase, they will rate global symptom severity, satisfaction with IBS symptoms, life interference, and mood using the abbreviated POMS, and time spent completing homework assignments. In addition, participants will complete process measures (IBS SE, WAI, IBS LOC, etc) at regularly scheduled times during active treatment phases. Participants should complete process measures within seven days of their being assigned.

- Two-week follow-up assessment The two-week assessment should occur two weeks from the date of the last active treatment session, plus or minus (+) two weeks.
- Three-month assessment The three-month assessment should occur three months ± two weeks from the date of the last active treatment session.
- Six-month assessment The six-month assessment should occur six months \pm two weeks from the date of the last active treatment session.
- Nine-month assessment The nine-month assessment should occur nine months ± two weeks from the date of the last active treatment session.
- 12-month assessment The 12-month assessment should occur 12 months \pm two weeks from the date of the last active treatment session.

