1.4 Objectives

- *Primary*: Evaluate the short-and long-term effects of a minimal-contact, homebased, patient-administered version of CBT compared to a standard, clinic-based, therapist-administered version of CBT and a psychological placebo (attention control) condition on improving global IBS symptoms.
- Secondary: To identify clinically useful patient characteristics associated with outcome as a way of gaining an understanding of subgroups of participants for whom CBT is most beneficial; to identify theory-based change mechanisms (active ingredients) that explain how and why CBT achieves therapeutic objectives; to evaluate the economic costs and benefits of CBT relative to control conditions.

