3.2 Secondary Objectives

Aim 2. To identify clinically useful participant characteristics associated with outcome as a way of gaining an understanding of subgroups of participants for whom CBT is most beneficial.

Hypothesis 1: Variables such as treatment motivation at baseline and rapid treatment response will be positively associated with treatment outcome after the acute treatment phase of CBT and through follow-up periods.

Hypothesis 2: Interpersonal distress and extra-intestinal medical problems at baseline will be negatively associated with treatment outcome after the acute treatment phase of CBT and through follow up.

Aim 3. To identify theory-based change mechanisms (active ingredients) that explain how and why CBT achieves therapeutic objectives.

Hypothesis 1: Changes in the severity of IBS symptoms are partly mediated by changes in participants' beliefs regarding the causality (locus of control) and controllability (self efficacy) of IBS symptoms.

Hypothesis 2: Changes in the severity of IBS symptoms are partly mediated by nonspecific factors such as a strong therapeutic alliance and positive expectancy of improvement.

Aim 4. To describe the cost and cost effectiveness of MC-CBT, S-CBT and attention placebo for IBS.

Hypothesis 1: MC-CBT is associated with decreased direct and indirect cost compared to SCBT and associated with increased direct and indirect cost compared to attention control.

Hypothesis 2: MC-CBT will prove cost effective relative to either S-CBT or attention control.

Aim 5. To assess long-term durability of acute treatment effects of CBT at 3-, 6-, 9-, and 12 month follow-ups.

Hypothesis: Participants assigned to both CBT conditions will maintain treatment gains with respect to attention placebo through quarterly follow-up periods extending to 12 months after treatment completion.

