3.3 Primary Efficacy Endpoints

The primary efficacy endpoint is as follows:

 Participant-rated global improvement of IBS symptoms. A participant is considered to be a treatment responder if s/he rates IBS symptoms for which s/he sought treatment as markedly to moderately improved using the Clinical Global Impressions Scale–IBS version.

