7.4. Formal Data Analysis

Aim 1

The primary focus of Aim 1 is to establish whether the effects of MC-CBT and S-CBT are comparable. We will pursue this from two perspectives: a traditional hypothesis testing framework and an equivalence testing framework. For the core outcome variables, we have assessments at baseline (BL), immediate post-test (FU W12) and at three-, six-, nine-, and 12-month follow-ups (FU3, FU6, FU9 and FU12) for each of three groups (MC-CBT, S-CBT and the active comparison control (attention control)). The traditional analysis for a given outcome variable is a two-way analysis of covariance

using the three groups as a between-participants factor, time as a within-participants factor (IM, FU3, FU6, FU9 and FU12) and the baseline score as a covariate. Single degree of freedom contrasts focus on the pair-wise comparisons of adjusted means within a given time period (e.g. comparing MC-CBT, S-CBT, and the attention control condition). Of interest is whether there are statistically significant pair-wise contrasts between the groups. We will pursue such contrasts using non-pooled error terms across time (because of the likely violation of sphericity), but with pooled error terms across groups within time (unless diagnostics suggest otherwise). We will use the program M Plus to estimate the single degree of freedom contrasts (by translating the analysis of covariance model into an SEM framework). M Plus has the capability to take into account cluster effects, should that be necessary, and it also offers robust algorithms.

In terms of statistical power, for a single degree of freedom contrast between two independent groups with a single covariate, the approximate sample size needed to achieve power of 0.80 for an adjusted mean difference of d = 0.50 (using Cohen's d) is approximately 65 per group. To achieve power of 0.90 requires a sample size of 85 per group. Our sample sizes easily meet these standards.

Aim 5

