The **Patient-Reported Outcome Interview** (IBS Module PRO-IBS) ⁵⁷ is a semistructured interview whose 7 core items and 9 associated items correspond to Rome III criteria for IBS.

The IBS-PRO, in conjunction with physician decision making, can be used to support a current diagnosis of IBS in accordance with Rome III criteria. In addition to assessing the frequency and impact (distress, functional limitations) of key IBS symptoms (abdominal pain/discomfort, altered defecation, and associated symptoms such bloating, incomplete evacuation, nausea, urgency), the PRO-IBS taps the global impact of IBS symptoms on social, home/family, and occupational functioning, improvement in symptoms since baseline administration, overall response validity, and overall IBS severity. For each item, standardized questions and probes are provided to elicit description of symptom. These probes are designed to elicit the experience of IBS symptoms and their impact from the patient's perspective. The PRO-IBS is designed to be administered by clinicians and clinical researchers who have a working knowledge of IBS and Rome diagnostic criteria as well experience performing semi-structured diagnostic evaluations. The less clinical experience the potential interviewer has had, the more training required.

Outcome Assessment

Global Improvement / Relief

Consistent with Rome III recommendations ⁵⁸, the primary endpoint will be global improvement/relief of IBS symptoms. Global improvement of IBS symptoms will be based on a patient's response to the seven-point ordinal **Clinical Global Improvement Scale** (CGI-I)⁵⁹: "Compared to how you felt prior to entering the study, how would you rate the IBS symptoms for which you sought treatment during the past week?" (1 = very much improved, 7 = very much worsened).

We will adopt the practice ^{44, 47, 60} of defining responders as participants with a score of 1 (much improved) or 2 (very much improved) on the CGI-I. At post-treatment assessments, the study gastroenterologists (blind to treatment allocation) will complete a clinician-rated version of the CGI-I ⁴⁸ to estimate how much the participants' IBS symptoms improved or worsened relative to his or her baseline state.

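### The primary responder rule is worded inconsistently and no primary visit is named, so the visit that carries the main result could be chosen after the data are seen

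*Protocol*

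**What the plan says.** **Responder rule.** Protocol Section 3.3: "A participant is considered to be a treatment responder if s/he rates IBS symptoms for which s/he sought treatment as markedly to moderately improved". The protocol does not say which scores these words cover. Appendix 8 (Global Improvement / Relief) introduces a seven-point scale with "1 = very much improved, 7 = very much worsened" and lists no anchors for points 2 to 6. It then defines responders as participants with a "score of 1 (much improved) or 2 (very much improved) on the CGI-I". The same subsection says that "the primary endpoint will be global improvement/relief of IBS symptoms", while Section 3.4 lists adequate relief as a secondary endpoint.

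**Time of assessment.** Section 3.3 names no visit, although Section 3.4 gives times for most secondary endpoints. The primary objective in Section 1.4 begins "Evaluate the short-and long-term effects of a minimal-contact". Section 3.2 lists as Aim 5, a secondary objective, "To assess long-term durability of acute treatment effects of CBT at 3-, 6-, 9-, and 12 month follow-ups". The Appendix 7 schedule collects the global impression form at all five follow-up visits.

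**Analysis.** Under Aim 1, Section 7.4 describes single-degree-of-freedom comparisons of the three arms within each of five post-treatment times (IM, FU3, FU6, FU9, FU12). It adds: "Of interest is whether there are statistically significant pair-wise contrasts between the groups". No visit or contrast is marked primary.

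**The concern.** A cut-off and a visit together determine what the primary result is. Here the cut-off is worded in two ways with no bridge between them, and the visit is open. Two analysts could follow this protocol faithfully and report different primary results.

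This goes beyond detail that a protocol may leave to an analysis plan, because the passages pull against each other. Long-term effects are primary in one section and secondary in another, and the scored rule contradicts its own scale. An analysis plan cannot follow both versions. The stakes are higher because participants rate this endpoint themselves and know which treatment they received.

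**Working it through.** **Step 1. Compare the responder definitions.**

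| Place | Rule | Scores |
|---|---|---|
| Section 3.3 | "markedly to moderately improved using the Clinical Global Impressions" scale | not given |
| Appendix 8, scale | "1 = very much improved, 7 = very much worsened" | 1 is the best category |
| Appendix 8, responder | "score of 1 (much improved) or 2 (very much improved) on the CGI-I" | 1 and 2, with labels reversed |

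Reversing the labels of 1 and 2 does not change the set {1, 2}, so it reclassifies nobody who is counted by score. The open question is whether the lower grade in Section 3.3 stops at score 2 or reaches score 3. With points 2 to 6 unlabelled, the document does not settle it.

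**Step 2. Reproduce the plan's own figure.** Section 7.4 gives about 65 per group (80% power) and 85 (90% power) for d = 0.50. Alpha is not stated; I assume 0.05 two-sided. With n = 2(z₀.₉₇₅ + z_power)² / d²:
- 80%: 2(1.960 + 0.842)² / 0.25 = 62.8, so 63 per group;
- 90%: 2(1.960 + 1.282)² / 0.25 = 84.1, so 85 per group.

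The stated figures reproduce to within two patients. They cover one contrast at one time.

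**Step 3. Count the contrasts.** Three pairwise comparisons × 5 visits = 15 per outcome. Of these, 2 CBT arms × 5 visits = 10 compare CBT with attention control.

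**Step 4. Error rate with the visit left open.** If the five visits were independent, one contrast would give 1 − 0.95⁵ = 22.6%. Repeated visits are correlated, so I simulated under the null: three arms, a shared control, five visits with equal correlation ρ, and 0.05 two-sided per test. The protocol gives no ρ; the range is an assumption.

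| Chance of a false positive | ρ = 0.5 | ρ = 0.7 | ρ = 0.8 |
|---|---|---|---|
| One CBT-versus-control contrast, any of 5 visits, either direction | 18% | 15% | 13% |
| Same, in favour of CBT (nominal 2.5%) | 9% | 7% | 6% |
| Any of the 10 CBT-versus-control contrasts, either direction | 31% | 26% | 22% |
| Both CBT arms beat control at a common visit, neither effective | 2.0% | 1.7% | 1.5% |

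**Step 5. Match these to Hypothesis 1.** Section 3.1 claims that both CBT arms are superior to control, so one significant contrast in ten does not establish it. When neither arm works, the last row applies and there is no inflation. When one arm clearly works and the other does not, the false claim rests on the ineffective arm alone. The second row is then the upper bound: about 6 to 9%, against 2.5% at one fixed visit.

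**The case against.** The strongest reply is that this is mostly clerical. Appendix 8 fixes the rule by score, the label swap changes nobody's status, and Section 3.3 names two grades of improvement just as Appendix 8 names two scores. They may be the same top two categories. That stands: a reader might infer two incompatible cut-offs, but the documents do not show that any patient is classified differently. Nor do they support a size for a cut-off shift. The share scoring 3 is not given, and moving a cut-off changes the rate in every arm, so only the change in the between-arm difference would matter.

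A second reply is that 22 to 31% overstates the problem. This also stands. A reader might take that figure as the trial's error rate, but it counts results favouring control and allows a win on either arm alone, whereas Hypothesis 1 needs both.

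Third, the contrasts in Section 7.4 are written for adjusted means with a baseline covariate. The primary endpoint is a responder status on a change scale with no baseline form, so applying those contrasts to it is an inference. That is fair, but it means Section 7.4 does not supply the missing primary test either.

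Finally, a multiplicity procedure may sit in an analysis plan that is not shown. Agreed, and the point does not rest on its absence. The responder rule and the primary visit define the endpoint, and the protocol is in conflict with itself on the rule's wording and on the status of long-term effects.

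**Conclusion.** The concern holds in this form: the primary responder definition is unmapped in Section 3.3 and mislabelled in Appendix 8, no primary visit is named, and Sections 1.4 and 3.2 disagree on whether long-term effects are primary. Freedom to choose the visit raises the false-positive chance for a single CBT-versus-control contrast to about 13 to 18%, of which about 6 to 9% favours CBT. For Hypothesis 1 as worded, 6 to 9% is an upper bound, reached when one arm works and the other does not. These sizes assume two-sided 0.05 per test, equal between-visit correlation of 0.8 to 0.5, and that the Section 7.4 contrasts are carried over to the responder endpoint. The textual conflicts need none of these assumptions.

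**What to change.** 1. State one score-based responder rule in both Section 3.3 and Appendix 8. The only scored rule for this scale in the document is CGI-I 1 or 2. Correct the labels to agree with the scale anchors, list all seven anchors, and either map the Section 3.3 wording to scores or remove it.
2. Name one primary visit before outcome data are seen. The week-12 post-treatment visit fits the existing aims, with the 3- to 12-month contrasts placed under Aim 5. Align Section 1.4 with this.
3. Test Hypothesis 1 at that visit by requiring both CBT arms to beat attention control. This needs no split of alpha.
4. State in Section 7.4 which test applies to the responder endpoint, since the covariance model there does not fit it directly.

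The cost is a wording amendment, with no new data and no change in sample size. The real loss is that later-visit contrasts are no longer confirmatory. If the sponsor wants long-term effects to stay primary, the protocol should say so and name the visit.
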